1. BACKGROUND MATERIAL

1.1 Graft vs. Host Disease

Acute graft vs. host disease (GVHD) caused by mature donor lymphocyte alloreactivity to host tissue antigens (Ags), following allogeneic blood and marrow transplantation (BMT) for hematologic malignancies, is a major cause of morbidity and mortality. Multiple organs can be involved, including the skin, liver, and lungs, but the main cause of death appears to be damage to the intestinal tract (IT) small and large bowel, resulting in sepsis, diarrhea, and shock [1, 2]. A prominent finding is loss of villous crypt Paneth cells, which produce antimicrobial alpha1 defensin [3]. Acute and chronic GVHD are prevented by purging donor hematopoietic cell transplants (HCTs) of mature lymphocytes prior to transplantation [4-6] but this leads to untenable rates of tumor relapse, due to loss of graft vs. tumor effect (GVTE), also mediated by mature donor lymphocytes (primarily T cells). In fact, an inverse correlation exists between severity of GVHD and incidence of relapse [7-9]. This conundrum has spurred efforts to mitigate GVHD while preserving GVTE.

1.2 Overcoming GVHD While Preserving GVTE

Removal of mature alloreactive donor T cells from allogeneic hematopoietic cell transplant (HCT) grafts prevents graft vs host disease (GVHD), but also eliminates graft vs. tumor effect (GVTE), resulting in unacceptable rates of cancer relapse. A solution to this conundrum appears to be possible. In mice, several different strategies for preventing intestinal tract (IT) reduce or eliminate GVHD mortality while preserving systemic alloreactivity and GVTE.

One strategy is to identify tumor specific Ags (TSAs) and the T cell clones recognizing them, so that these may be selectively expanded, while all other alloreactive clones are removed [10, 11]. The limited number of well-defined TSAs is an obstacle to this approach. So, too, is the removal of alloreactivity, which comprises a much broader, stronger, and less readily evaded response repertoire than that generated against a single TSA. Therefore, our long term objective is to ameliorate IT GVHD, while preserving highly effective systemic alloreactive GVTE.

Four general strategies can be envisioned for protecting the gut against GVHD while preserving general alloreactivity: 1) Reduce accumulation of alloreactive effector lymphocytes at the most vulnerable IT sites via tighter endothelial barriers, decreased diapedesis and motility of alloreactive T cells (Teffs), and/or decreased gut-specific homing. 2) Inhibit IT neo-vascularization by donor derived endothelial cells (ECs) differentiating from precursors (EPCs) under hypoxic conditions—recently revealed to be a major source of IT pathology during GVHD [12-15]. 3) Activate and expand allospecific IT regulatory T cells (Tregs) to suppress the inflammatory and cytotoxic responses of effector T cells (Teffs) in a localized manner. In this scenario, Tregs protect the most vulnerable GVHD sites (gut mucosa), while alloreactive Teffs remain in circulation throughout the rest of the body, available to encounter and eliminate residual host derived tumor cells. 4) Reduce intestinal leakage of bacteria and bacterial products such as endotoxin, which induce local and systemic inflammation at sites of GVHD.

The potential utility of the first approach is supported by dramatically reduced GVHD in mice receiving allogeneic cells from donors genetically defective for gut homing integrin $\alpha 4\beta 7$ [16], or retinoic acid receptors which transduce signals leading to $\alpha 4\beta 7$ upregulation [2]. Comparable protection against IT GVHD was seen when allograft donor lymphocytes were depleted of $\alpha 4\beta 7$ + populations *prior* to transplantation [16]. In these three cases where $\alpha 4\beta 7$ mediated gut homing cells were absent, host syngeneic tumors were still strongly rejected. In transplant patients, maraviroc (a CCR5 blocker) prevented IT GVHD and acute (within 100 days) death, but was associated with ~20% greater relapse at 1 year (vs. historical controls) – not statistically significant, but suggestive of immune suppression with respect to GVTE, perhaps due to the widespread distribution of CCR5 on immune cells [17].

The potential utility of the second strategy (inhibition of neovascularization) is supported by analogous mouse studies with anti-vascular endothelial (VE)-cadherin mAb, which reduced IT neovascularization and IT GVHD while leaving anti-tumor alloreactivity intact [15]. Blocking hypoxia-induced neovascularization with other agents capable of decreasing IT hypoxia and neovascularization (e.g. telmisartan) may provide similar benefits.

The third approach also appears promising, based on clinical studies. Crowe's group demonstrated an inverse correlation between T regs bearing IT homing receptors $\alpha 4\beta 7$ and acute GVHD in patients [18, 19]. Addition of donor Tregs (not $\alpha 4\beta 7$ selected) suppressed GVHD without significant early interference with anti-tumor immunity [20]. Selective injection of $\alpha 4\beta 7$ Tregs does not appear to have been attempted, but, presumably, would be beneficial with respect to IT GVHD without suppressing systemic GVTE. There is clinical evidence that telmisartan may increase Treg levels and function, while reducing self-reactive T17 cells [21]. Thus, it is possible that telmisartan will also increase the ratio of Treg : alloreactive T effectors.

The fourth approach has been supported by numerous pre-clinical and clinical studies showing reduced GVHD in mice and patients pre-treated with gut sterilization, or in some cases, probiotics prior to allogeneic transplantation, and by studies showing that inhibition of rho kinase prevents intestinal leak syndrome after irradiation [22], and that telmisartan ameliorates colon inflammation in experimental colitis in rodents [23].

1.3 Telmisartan

1.3.1 Mechanisms of action

Telmisartan (Micardis) was developed and FDA approved and licensed as an angiotensin receptor blocker (ARB). It has been safely used for > 18 years as an anti-hypertensive drug. Importantly, immune suppression has not been reported as an increased risk during the post-marketing period. About 6 years ago, it was discovered that telmisartan has a second mechanism of action that may account for much of its anti-hypertensive activity. It was found to be an agonist for peroxisome proliferator activated receptor gamma (PPAR γ). PPAR γ agonists (e.g. glitazone) are used as insulin sensitizing drugs to treat type 2 diabetes, and also have anti-hyperlipidemia benefits. More recently, the anti-inflammatory functions of PPAR γ agonists have been elucidated. Some of these anti-inflammatory effects appear to be due to reduction in the activity of rho associated coiled coil kinase (rho kinase, or ROCK). In fact, telmisartan was found to be as

Telmisartan for GVHD in HCT

potent an inhibitor of ROCK as Y27632, a specific ROCK inhibitor [24]. Thus, the anti-hypertensive effects of telmisartan are now thought to reflect the combination of ARB, PPAR γ activation, and ROCK inhibition.

Because recognition of telmisartan as a PPAR γ agonist has been slow, and its potency as a ROCK inhibitor is still not widely appreciated, many of the obvious pre-clinical and clinical trials have not been done. Additionally, there may be concerns that any positive effects will not be cleanly attributable to a single mechanism of action. In the case of GVHD, however, this poses no problem. We have demonstrated protection from GVHD by the ROCK inhibitor, fasudil, similar in potency and mechanism of action to Y27632 [25] (and see below). Meanwhile rosiglitazone, a specific PPAR γ agonist, has been shown to suppress GVHD inflammation in a similar mouse model although survival curves were not followed [26]. Telmisartan's protective effect in experimental rat colitis has been noted, above [23]. Thus, telmisartan is likely to be an effective drug for the treatment and prophylaxis of GVHD, by PPAR γ activation *and* downstream ROCK suppression.

With respect to mechanism(s), there is potential for inhibition of T cell migration, as telmisartan abrogates lymphocyte chemotaxis, in part by abrogation of SDF-1 induced chemotaxis [27]. Additionally, telmisartan may maintain gut endothelial barriers by protecting endothelial cells (ECs) from inflammation mediated destruction [28, 29]. Telmisartan has also been shown to prevent neovascularization in corneal systems [30, 31]. Finally, as noted, telmisartan has been shown to increase the ratio of protective Tregs : autoreactive Th17 cells [21], and a very recent report demonstrates anti-inflammatory effects of telmisartan in the setting of chemically induced acute colitis [23]. Multiple genetic pathways activated by inflammation and oxidative stress, along with inflammatory cell infiltrates and gross pathology of weight loss and diarrhea, were attenuated by pre-treatment with telmisartan. Considering the shared pathways between colitis and acute IT GVHD, this is encouraging.

Additional support for the use of telmisartan comes from a review of the literature, and our own work, on ROCK and its inhibitors, fasudil and Y27632. These have been much more extensively studied than telmisartan, over the past two decades, with respect to the three protective mechanisms envisioned. Fasudil occupies the ATP binding pocket of ROCK's enzymatically functional kinase domain, thereby preventing its phosphorylation of myosin light chain II (MLC) and MLC phosphatase (MLCP) [32-34]. Phosphorylation of MLC activates it for actin filament binding and ratcheting, while phosphorylation of MLCP prevents this enzyme from de-phosphorylating (inactivating) MLC. Thus, ROCK potentiates smooth muscle contraction from two angles, both inhibited by fasudil. This explains fasudil's anti-spasmodic properties on arterial smooth muscle, and its anti-hypertensive effects in pre-clinical and clinical studies [35-42], as well as anti-asthmatic effects in OVA induced asthma models [43]. Fasudil, unavailable for clinical use in Europe or USA, has been safely used in Japan and other Asian countries for almost two decades without evidence of immune suppression.

MLC phosphorylation is also important in the context of cell motility and signal transduction. Over the past 15 years, numerous cell functions were shown to be ROCK dependent, including leukocyte chemotaxis, diapedesis, cytokine secretion and responsiveness [44-52], and tumor cell invasiveness and metastasis [53-65]. Additional targets of ROCK **ser / thre** kinase activity include

cytoskeletal ezrin, radixin, moesin, and focal adhesion kinase [66]. Further, ROCK inhibits endothelial nitric oxide synthase (eNOS) production of NO [67, 68]. Thus, it decreases blood flow in NO regulated vascular beds. ROCK inhibition **increases** blood flow in NO regulated vasculature, and also appears to enhance the integrity of endothelial barriers, decreasing capillary leakage and endocyte apoptosis [44-52, 69-71]. Additionally, ROCK inhibition antagonizes vascular endothelial growth factor (VEGF) by more than one pathway [72-78]. Finally, a recent paper indicates that, in the context of experimental autoimmune encephalomyelitis, ROCK inhibition promotes T reg differentiation by shifting macrophages from M1 to the Treg inducing M2 phenotype [79].

Given these functions, net effects of ROCK inhibition by telmisartan in the context of allogeneic BMT plus tumor burden could include: i) decreased inflammatory donor cell migration to, penetration of, and inflammation within key target organs of GVHD; ii) vasodilation, decreased hypoxia, and reduced IT neovascularization; iii) decreased Teff function, possibly due to iv) increased Tregs, and v) anti-tumor effects. Indeed, there is pre-clinical evidence suggesting a potential anti-tumor effect of telmisartan [80].

1.3.2 Clinical experience with Micardis brand of telmisartan

Telmisartan has not been previously used for the specific purpose of preventing or ameliorating GVHD.

Telmisartan is used clinically for hypertension and prophylaxis of heart attacks at doses ranging from 20 mg to 160 mg. Typically, patients whose hypertension remains uncontrolled on 80 mg will be given a combination of telmisartan and hydrochlorothiazide in mg combinations of the two drugs at 80/12.5, 80/25, or 160/25.

The onset of antihypertensive activity occurs within 3 hours after administration of a single oral dose. At doses of 20, 40, and 80 mg, the antihypertensive effect of once daily administration of telmisartan is maintained for the full 24-hour dose interval. With automated ambulatory blood pressure monitoring and conventional blood pressure measurements, the 24-hour trough-to-peak ratio for 40 to 80 mg doses of telmisartan was 70 to 100% for both systolic and diastolic blood pressure.

The incidence of symptomatic orthostasis after the first dose in all controlled trials was low (0.04%). Upon initiation of antihypertensive treatment with telmisartan, blood pressure was reduced after the first dose, with a maximal reduction by about 4 weeks. Most of the BP lowering effect occurs within the first 2 weeks of treatment. With cessation of treatment with micardis tablets, blood pressure gradually returned to baseline values over a period of several days to one week. The antihypertensive effect of telmisartan is not influenced by patient age, gender, weight, or body mass index. Blood pressure response in black patients (usually a low-renin population) is noticeably less than that in Caucasian patients. Limited data are available with regard to overdosage in humans. The most likely manifestation of overdosage with MICARDIS tablets would be hypotension, dizziness and tachycardia; bradycardia could occur from parasympathetic (vagal) stimulation.

1.3.3 Drug interactions and cautions

Telmisartan is contraindicated during pregnancy, and no subjects will be enrolled if there is a chance of pregnancy during the telmisartan treatment phase of the trial. We do not anticipate any such volunteers in an HCT based study, because all female HCT patients who have not been menopausal for at least 1 year, have been serum screened with serum pregnancy tests and are placed on high dose Ovril to prevent pregnancy, which will continue for the 100 days' duration of telmisartan administration, as per Standard Operating Procedures (SOP). Similarly, women are told not to breast feed children during HCT as per SOP. Any women who choose to nurse children will not be eligible for the study, or will be removed from the study if they have started to matriculate.

In patients with an activated renin-angiotensin system, such as volume- or salt-depleted patients (e.g., those being treated with high doses of diuretics), symptomatic hypotension may occur after initiation of therapy with telmisartan. We will take patients off their non-telmisartan anti-hypertensives for two days prior to administration of telmisartan. Blood chemistries, blood pressure, and urination frequency will be monitored to ensure adequate hydration and normokalemia prior to starting telmisartan. For patients already taking telmisartan as part of their normal medical regimen, their daily dose will be replaced by the starting dose of 160 mg and adjusted as needed (see section 5.3.3.). Patients who require additional anti-hypertensive medications will have an appropriate drug added. For example, hydrochlorothiazide and aldosterone have been used in standardized ratios with telmisartan.

Hyperkalemia may occur in patients on telmisartan, particularly in patients with advanced renal impairment, heart failure, on renal replacement therapy, or on potassium supplements, potassium-sparing diuretics, potassium-containing salt substitutes or other drugs that increase potassium levels.

As the majority of telmisartan is eliminated by biliary excretion, patients with biliary obstructive disorders or hepatic insufficiency can be expected to have reduced clearance.

As a consequence of inhibiting the renin-angiotensin-aldosterone system, changes in renal function may occur in susceptible individuals. In patients whose renal function may depend on the activity of the renin-angiotensin-aldosterone system (e.g., patients with severe congestive heart failure or renal dysfunction), treatment with angiotensin receptor antagonists has been associated with oliguria and/or progressive azotemia and (rarely) with acute renal failure and/or death. Patients with such pre-existing conditions would not be candidates for HCT, in any case.

In patients who are elderly, volume-depleted (including those on diuretic therapy), or with compromised renal function, co-administration of NSAIDs, including selective COX-2 inhibitors, with telmisartan, may result in deterioration of renal function, including possible acute renal failure. These effects are usually reversible. The antihypertensive effect of angiotensin II receptor antagonists, including telmisartan may be attenuated by NSAIDs including selective COX-2 inhibitors.

Aliskiren is associated with increased risks of hypotension, hyperkalemia, and changes in renal function (including acute renal failure) compared to monotherapy. Patients cannot be on Aliskiren while on the study. Aliskiren should not be co-administered with Micardis in patients with diabetes.

When Micardis was co-administered with digoxin, median increases in digoxin peak plasma concentration (49%) and in trough concentration (20%) were observed. Therefore, we would monitor digoxin levels when initiating, adjusting, and discontinuing telmisartan for the purpose of keeping the digoxin level within the therapeutic range.

Reversible increases in serum lithium concentrations and toxicity have been reported during concomitant administration of lithium with angiotensin II receptor antagonists including Micardis. Therefore, we will monitor serum lithium levels during concomitant use.

Co-administration of telmisartan 80 mg once daily and ramipril 10 mg once daily to healthy subjects increases steady-state C_{max} and AUC of ramipril 2.3- and 2.1-fold, respectively, and C_{max} and AUC of ramiprilat 2.4- and 1.5-fold, respectively. In contrast, C_{max} and AUC of telmisartan decrease by 31% and 16%, respectively. When co-administering telmisartan and ramipril, the response may be greater because of the possibly additive pharmacodynamic effects of the combined drugs, and also because of the increased exposure to ramipril and ramiprilat in the presence of telmisartan. Concomitant use of Micardis and ACE inhibitors such as ramipril is not permitted on this study.

Drugs **without** known telmisartan interactions include: acetaminophen, amlodipine, glyburide, simvastatin, hydrochlorothiazide, warfarin, and ibuprofen. Telmisartan is not metabolized by the cytochrome P450 system and had no effects in vitro on cytochrome P450 enzymes, except for some inhibition of CYP2C19. Telmisartan is not expected to interact with drugs that inhibit cytochrome P450 enzymes; it is also not expected to interact with drugs metabolized by cytochrome P450 enzymes, except for possible inhibition of the metabolism of drugs metabolized by CYP2C19.

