4.1.1 Inclusion Criteria

Subjects must meet all of the following inclusion criteria to be eligible for enrollment into the study:

1. Meet the eligibility criteria for HCT as defined by the Standard Operating Procedures (SOP) of the blood and marrow transplantation program of Hackensack University Medical Center.

2. Diagnosis of:

- Acute myeloid or lymphoid leukemia in remission,
- Myelodysplastic syndrome,
- Chronic lymphoid leukemia,
- Non-Hodgkin lymphoma,
- Hodgkin lymphoma,
- Chronic myeloid leukemia in chronic or accelerated phase,
- Myeloproliferative disorder, or
- Multiple myeloma

3. Undergoing allogeneic HSC transplantation from a related or unrelated donor matched at least at 7 of 8 of the HLA-A, -B, -C, and DR loci (“8/8” or “7/8” match)

4. Planned to receive standard GvHD prophylaxis regimen. Subjects receiving rabbit ATG (Thymoglobulin) as part of their conditioning regimen are eligible to participate.

5. Male or female patient age 18 years or older

6. Karnofsky performance status $\geq 70\%$ at time of initiation of pre-transplant conditioning

7. Transplantation-specific co-morbidity score of <5 at time of initiation of pre-transplant conditioning

8. Patients taking antihypertensive medications (including telmisartan) are eligible but the patient must discontinue treatment at least 48 hours prior to first dose of study medication. In cases where the patient’s physicians feel it would be inadvisable to stop all anti-hypertensive treatment prior to starting telmisartan, the patient may continue on amlodipine, hydrochlorothiazide, furosemide, or other non-ARB, non-ACE inhibitors, or non-potassium sparing anti-hypertensives. If ARBs, ACE inhibitors, renin inhibitors, spironolactone, or other potassium sparing drugs cannot be discontinued prior to starting telmisartan, the patient will be ineligible for the study.

9. Capable of giving informed consent and having signed the informed consent form

4.1.2 Exclusion criteria:

Subjects who meet any of the following exclusion criteria will not be eligible for enrollment in this study:

1. Inability to provide informed consent

2. Subjects with known heart failure, advanced renal impairment requiring renal replacement therapy, or liver failure although these patients would most likely not be eligible for HCT, as per SOP of the blood and marrow transplantation program of Hackensack University Medical Center.

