3. Subjects taking ACE inhibitors, ARBs, renin inhibitors, potassium supplements, or spironolactone (or any other potassium-sparing diuretics) who cannot discontinue use prior to initiation of study treatment OR who require a high-potassium diet.
4. Patient unable to discontinue current ARB, ACE inhibitor, renin inhibitors, spironolactone, or other potassium sparing hypertension medication for medical or other reasons for two days prior to starting telmisartan
5. Chronic symptomatic hypotension, volume depletion.
6. Planned to receive GvHD prophylaxis regimen with an investigational agent.
7. Pregnant or likely to become pregnant during the period of study, or unwilling to stop nursing.

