5.4.2 Agents That Increase the Risk of Renal Failure

Hyperkalemia may occur in patients on telmisartan, particularly in patients with advanced renal impairment, heart failure, on renal replacement therapy, or on potassium supplements, potassium-sparing diuretics, potassium-containing salt substitutes or other drugs that increase potassium levels. Potassium-sparing diuretics such as spironolactone, and angiotensin-

converting-enzyme (ACE) inhibitors will be discontinued prior to start of study and will not be used in conjunction with telmisartan during the study unless deemed necessary by the HCT clinical physicians, due to potential interactions leading to renal toxicity. Potassium supplements will also be discontinued, and re-started gradually if need is indicated by electrolyte monitoring. Foods high in potassium will be limited to safe levels during the period of telmisartan administration except as specifically allowed by the physician monitoring the patient's electrolyte status.

In patients who are elderly, volume-depleted (including those on diuretic therapy), or with compromised renal function, co-administration of NSAIDs, including selective COX-2 inhibitors, with telmisartan, may result in deterioration of renal function, including possible acute renal failure. These effects are usually reversible. Caution will be taken when administering NSAIDs to study subjects, and renal functions will be monitored.

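### ACE inhibitors with telmisartan are banned outright in section 1.3.3 but allowed at physician discretion in section 5.4.2, with no potassium or creatinine check tied to that exception

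*Combined protocol and SAP*

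**What the plan says.** **Section 1.3.3.** After describing the interaction with ramipril, the protocol sets a study rule: "Concomitant use of Micardis and ACE inhibitors such as ramipril is not permitted on this study". For potassium-sparing diuretics the same section warns of hyperkalemia but sets no ban.

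**Section 5.4.2.** Potassium-sparing diuretics and ACE inhibitors are to be stopped before the study and "will not be used in conjunction with telmisartan during the study unless deemed necessary by the HCT clinical physicians". The stated reason is possible renal toxicity from the interaction.

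**Entry rules.** Inclusion criterion 8 (4.1.1) reads: "If ARBs, ACE inhibitors, renin inhibitors, spironolactone, or other potassium sparing drugs cannot be discontinued prior to starting telmisartan, the patient will be ineligible". Exclusion criterion 4 (4.1.2) covers a "Patient unable to discontinue current ARB, ACE inhibitor, renin inhibitors, spironolactone, or other potassium sparing hypertension medication for medical or other reasons" in the two days before telmisartan. Section 5.4.1 leaves these classes out of the antihypertensives that may be continued without washout.

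**Monitoring tied to other drugs.** For digoxin, "we would monitor digoxin levels when initiating, adjusting, and discontinuing telmisartan". For lithium, "Therefore, we will monitor serum lithium levels during concomitant use". For NSAIDs, "Caution will be taken when administering NSAIDs to study subjects, and renal functions will be monitored".

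**Monitoring for everyone.** Section 6.3 and Table 3 require a chemistry panel at Day +7 and at every later study visit.

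**The concern.** A patient who comes to need an ACE inhibitor during the dosing period can be handled in opposite ways, depending on which section the treating team follows. Under 1.3.3 the combination is a protocol violation. Under 5.4.2 it is allowed on clinical judgement alone. If it is given, the protocol calls for no test because of it, although it names the kidney as the organ at risk.

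Patient safety and consistent conduct are at stake. The protocol's own account of the interaction explains why the restriction is there. With telmisartan 80 mg and ramipril 10 mg in healthy subjects, ramipril Cmax and AUC rose 2.3- and 2.1-fold, ramiprilat Cmax and AUC rose 2.4- and 1.5-fold, and the combined effect was described as possibly additive.

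**Working it through.** The plan gives no figure to reproduce here. The check is a comparison of text, followed by a count of days from the visit schedule.

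**Step 1: the rules side by side**

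| Section | ACE inhibitors | Potassium-sparing diuretics | When it applies |
|---|---|---|---|
| 1.3.3 | Banned, no exception | Hyperkalemia warning, no ban | On study |
| 4.1.1 (criterion 8), 4.1.2 (criteria 3 and 4) | Must be stopped, or patient is ineligible | Same | At entry |
| 5.4.1 | Not among drugs that may continue | Same | At start of dosing |
| 5.4.2 | Not used, unless transplant physicians judge it necessary | Same | On study |

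Only 1.3.3 and 5.4.2 speak to ACE inhibitors during the study in general terms, and they disagree. The entry rules do not govern a drug started later. They do show that medical need was not accepted as a reason for an exception at entry. For potassium-sparing diuretics there is no contradiction with 1.3.3. The point there is only that the 5.4.2 exception carries no condition.

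**Step 2: is a check attached to the exception?** Section 5.4.2 mentions electrolyte monitoring in connection with potassium supplements and high-potassium foods, and renal monitoring in connection with NSAIDs. Section 1.3.3 asks for chemistries and normokalemia before telmisartan is started. None of these is a test after an ACE inhibitor or potassium-sparing diuretic is added.

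**Step 3: how long until the next required panel?** Inputs are dosing from Day -2 to Day +98 (5.1) and required panels at Day +7, weekly to Day +56, then Days +70, +84 and +100 (6.3, Table 3). Table 3 marks no panel between screening and Day +7. The wait is the day of the next panel minus the day the drug is started, on nominal visit days.

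- Started Day -2: 7 - (-2) = 9 days.
- Started the day after a weekly panel, Day +7 to Day +56: 7 - 1 = 6 days.
- Started Day +57: 70 - 57 = 13 days.
- Started Day +71: 84 - 71 = 13 days.
- Started Day +85: 100 - 85 = 15 days.

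For the first five subjects, who start on Day -5, the earliest case is 7 - (-5) = 12 days. The visit windows of ±3 days would shift these figures. They are the longest nominal waits within each stretch.

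**The case against.** The strongest case against is that the protocol already surrounds these patients with oversight, and that 5.4.2, as the operational section, can be read as the governing rule.

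Much of the first part stands. Chemistry panels are scheduled throughout, and 6.3 allows further tests as standard care. Blood pressure is taken every 4 hours in hospital and twice daily at home. Concomitant medications are reviewed continuously. Section 4.2.2 asks outside physicians not to prescribe additional medicines while the patient is on telmisartan. Section 5.4.2 refers to a physician who monitors electrolytes. Section 5.3.4 cuts the dose after grade 3 or greater hypotension or drug-related events. A reader might infer that potassium and renal function go unmonitored, and the documents do not support that. What remains is that none of these measures says which rule applies, and none requires a test because such a drug was started.

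The second part does not stand. The protocol states no order of precedence between sections. The sentence in 1.3.3 is worded as a study rule, not as background.

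Four other stronger readings should be set aside:

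- **No way to stop telmisartan.** Section 5.5.1 already lets the investigator withdraw a subject from study treatment when medically necessary.
- **Potassium supplements as a model for a follow-up check.** The text is: "Potassium supplements will also be discontinued, and re-started gradually if need is indicated by electrolyte monitoring". It uses monitoring to show the need to restart. It does not prescribe a test afterwards.
- **Section 5.4.1 opens the door through compatible add-on antihypertensives.** The preceding paragraph of that section names these classes as not allowed to continue, so that reading is strained.
- **Sparser panels after Day +56 as a measure of risk.** Without a frequency of use, the spacing shows only when a required test would fall.

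**Conclusion.** The concern holds in a limited form. For ACE inhibitors, 1.3.3 and 5.4.2 give incompatible instructions in current text, and no other section reconciles them. For both classes, the 5.4.2 exception has no potassium or creatinine check, threshold or telmisartan rule attached.

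The size that can be shown is the wait for the next required panel: 9 days for a Day -2 start, 6 days between Day +7 and Day +56, and 13 to 15 days after that. This assumes nominal visit days, a start at the least favourable point, and no extra panels from standard care. The documents do not say how many patients would need these drugs, so no number of patients or events is claimed. Nothing is inferred about exposure at 160 mg from the 80 mg ramipril data.

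This is a safety and conduct inconsistency that the sponsor should correct. It does not affect the tests or power.

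**What to change.** **Preferred.** In 5.4.2, delete the physician-discretion clause that ends the passage "will not be used in conjunction with telmisartan during the study unless deemed necessary by the HCT clinical physicians", so that the section matches 1.3.3. Add that if an ACE inhibitor or potassium-sparing diuretic becomes necessary, telmisartan is held or stopped and the patient is followed to Day +180.

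A hold needs one further change. Section 5.3.3 counts five missed doses in any 2 weeks, for reasons other than hypotension or side effects, as non-compliance, and withdraws the patient if this happens before Day +14. A hold directed by the physician should be exempted from that count. A discontinuation before Day +14 would still lead to replacement under 5.5.2.

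**Alternative.** Keep the exception, cross-reference it in 1.3.3, and require potassium and creatinine checks at set times after the drug is started, without waiting for the next scheduled visit.

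**Cost.** One amendment with short wording changes: 5.4.2 and 5.3.3 for the preferred option, or 1.3.3 and 5.4.2 for the alternative. Under the first, a few patients may interrupt or stop telmisartan early, and any who stop before Day +14 would be replaced. Under the second, a few patients would have extra chemistry panels.
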